7.5. Ongoing Follow-Up Visits

It is anticipated that each subject will be seen at least once per year for a follow-up check-up.

The following follow-up data, as available, will be collected for each subject:

- Potentially related or directly related delayed cryoablation adverse events
- Lab assessments (creatinine, estimated GFR)
- Imaging results
- Biopsy/pathology results if available
- Assessment of disease progression, including retreatment
- Emergence of a new renal lesion
- Emergence of new neoplastic disease (any type)
- Emergence of metastatic disease
- Quality of Life Assessment (SF-12) at 6 and 12 months post procedure

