6.2 Time Point Algorithms

6.2.1 Relative Days

Relative days will be calculated for both efficacy and safety endpoints. The date of cryoprocedure will be considered relative day 1, and the day before the cryoprocedure will be relative day -1. Patients could also have received subsequent cryoprocedures, and these are recorded in the eCRF page named “Follow-up/Further Cancer Therapy” and not on an additional eCRF page named “Cryotherapy Procedure.” For the purposes of this SAP, date of cryoprocedure refers to the date of the first cryoprocedure. Relative days will be calculated as follows only when the full assessment date is known (i.e., partial dates will have missing relative days):

For days on or after cryoprocedure:

Date of assessment – Date of cryoprocedure + 1

For days before cryoprocedure:

Date of assessment – Date of cryoprocedure

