A lesion is considered to have post-cryoablation recurrence with enhancement if the response to the question “What is the status of the lesion?” in the follow-up lesion assessment eCRF page, is “Recurrent” and the response to the question “If Progressing or recurrent, was the lesion identified by contrast enhancement?” is “Yes” in the follow-up lesion assessment eCRF page. This endpoint will be recorded separately for each lesion.

A lesion is considered to have post-cryoablation progression with enhancement if the response to the question “What is the status of the lesion?” in the follow-up lesion assessment eCRF page, is “Progressing” and the response to the question “If Progressing or recurrent, was the lesion identified by contrast enhancement?” is “Yes” in the follow-up lesion assessment eCRF page. This endpoint will be recorded separately for each lesion.

In order to perform a per-patient analysis, for patients with multiple lesions, the lesion with maximum greatest trans-axial diameter will be considered.

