8.6 Analysis of Efficacy Parameters

8.6.3 *Change in lesion size*

Change from baseline and percentage change from baseline in lesion size will be summarized with descriptive statistics for each follow-up visit. This will be done separately for greatest trans-axial diameter and for lesion volume. A per-lesion and a per-patient analysis of change in lesion size will be provided.

Waterfall plots of the percentage change in the lesion size, as measured by greatest trans-axial diameter, will be given for each follow-up visit.

8.6.4 *Post-cryoablation lesion recurrence with enhancement and lesion progression with enhancement*

The number and percentage of patients with post-cryoablation lesion recurrence with enhancement, and the number and percentage of patients with post-cryoablation lesion progression with enhancement, (as defined in Section 6.4.2) will be given for each follow-up visit. The percentage will be based on the number of patients who remain in follow-up at that visit (i.e. excluding patients who have withdrawn, died or completed after the end date of the analysis window). For example, if a patient withdrew from the study or died within the 36 month analysis visit window, the patient would be included in the 36 month visit percentage calculation, but would not be included in the percentage calculations for subsequent visits.

This analysis will also be performed for the following subgroups:

- NS complexity categories at baseline
- Procedure method
- Lesion size at baseline, by greatest trans-axial diameter, as categories of ≤ 4 cm and > 4 cm
- Comorbidities (human immunodeficiency virus [HIV]/immunocompromised; diabetes; hypertension; obesity; blood clotting disorder; abdominal surgery; cardiovascular; retroperitoneal surgery; von Hippel-Lindau; cancer, other than renal)
- Patients who did and did not receive subsequent cryoablation (note: these patients will need to be identified manually from the response to the ‘Specify type of local or systemic therapy’ field on the ‘Follow-up/Further cancer therapy’ eCRF page)
- Area suspicious for lesion recurrence (yes, no) (as defined in Section 6.4.1) at the same post-cryoablation visit
- Baseline lesion classification (i.e., exophytic, mesophytic, endophytic)

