8.8.2 New therapies for renal cancer

The analyses described in this section will be performed on the ITT and RCC populations, separately for each visit.

The following will be summarized by the number and percentage of patients:

- Disease free status
- Patients who received a new therapy for renal cancer
- Patients who received local and systemic therapy

- Patients who received subsequent cryoablation (note: these patients will need to be identified manually from the response to the ‘Specify type of local or systemic therapy’ field on the ‘Follow-up/Further cancer therapy’ eCRF page)

Duration (months) between date of cryoprocedure and date of new local therapy will be summarized with descriptive statistics. Also, the duration (months) between dates of first and subsequent cryooperations (retreatments) will be summarized.

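### SAP 8.6.4 splits per-visit recurrence rates by subsequent cryoablation with no time anchor, so the groups can depend on an event that comes after the outcome

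*SAP*

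**What the plan says.** The output in SAP 8.6.4 is given for each follow-up visit: "The number and percentage of patients with post-cryoablation lesion recurrence with enhancement", and the same for progression with enhancement. The denominator rule is "The percentage will be based on the number of patients who remain in follow-up at that visit". It removes patients who have withdrawn, died or completed, and does not mention retreatment. The endpoint is defined in SAP 6.4.2: "A lesion is considered to have post-cryoablation recurrence with enhancement if the response to the question" on lesion status is Recurrent and the lesion was identified by contrast enhancement.

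The table is then repeated by subgroup, one of which is "Patients who did and did not receive subsequent cryoablation". A note adds that "these patients will need to be identified manually from the response to the" field that specifies the local or systemic therapy. No landmark, restriction to visits after retreatment, censoring at retreatment or caveat is given.

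Three other places matter:
- Protocol 7.5 lists among the follow-up data "Assessment of disease progression, including retreatment".
- SAP 8.8.2, under new therapies for renal cancer, counts patients with subsequent cryoablation and says that "the duration (months) between dates of first and subsequent cryooperations (retreatments) will be summarized".
- SAP 6.2.1 states that "date of cryoprocedure refers to the date of the first cryoprocedure", so visits stay anchored on the first procedure for retreated patients too.

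**The concern.** A subgroup split is readable when membership is settled before the outcome is observed. Most of the subgroups in SAP 8.6.4 meet that test: nephrometry complexity, procedure method, baseline lesion size, comorbidities and baseline lesion classification. The Hounsfield-unit subgroup is also post-treatment, but it is tied explicitly to the same visit. The repeat-cryoablation subgroup has no such tie.

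Read as ever/never, membership at Month 6 can be decided by something that happens at Month 14. If recurrence is a common reason to re-ablate, the columns sort patients partly by the outcome being counted. The retreated column also mixes images taken before and after the second procedure, because visits are not re-anchored.

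At stake is how the never-retreated column gets used. It invites reading as the recurrence rate after a single treatment, although the re-ablated failures have been taken out of it. The registry is meant to evaluate effectiveness (SAP 4.1), and its results are to be presented and published (Protocol 14), so a descriptive percentage may still be quoted.

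**Working it through.** The plan has no figure to reproduce: neither document states a recurrence rate, a retreatment rate or a power calculation. Every rate below is an assumption; only the planned size of about 250 comes from the documents.

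**Step 1: who sits where.** Take a patient with recurrence at Month 12 who is re-ablated at Month 14. Under ever/never the patient is in the retreated column at Months 6 and 12, before any retreatment, and is absent from the never-retreated column throughout.

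**Step 2: direction, cumulative form.** Let r be the probability of recurrence, a the probability of repeat cryoablation given recurrence, and b the same without recurrence.
- Rate in the retreated: ra / (ra + (1 − r)b).
- Rate in the never-retreated: r(1 − a) / (1 − ra − (1 − r)b).

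With r = 10% and a = 50%:

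| b | Retreated | Never retreated |
|---|---|---|
| 0 | 0.05/0.05 = 100% | 0.05/0.95 = 5.3% |
| 1% | 0.05/0.059 = 84.7% | 0.05/0.941 = 5.3% |
| 3% | 0.05/0.077 = 64.9% | 0.05/0.923 = 5.4% |

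Over r = 3–15%, a = 30–80% and b = 0–3%, the retreated show 24–100% and the never-retreated 0.6–11.3%. In every case the first lies above the true r and the second below it. The two agree only if a = b, that is, if retreatment is unrelated to recurrence.

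**Step 3: the table as planned, per visit.** The planned table is not cumulative, so the direction was checked by simulation: six visits, 300,000 patients per scenario, no attrition, and the same effect of the first procedure for everyone. Assumptions: new recurrence 1–2% per visit; re-ablation after a newly seen recurrence 30–80%; re-ablation without recurrence 0–2% in total; retreatment clears the lesion; an untreated recurrence either persists at later visits or is counted once.

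| | Ever retreated | Never retreated |
|---|---|---|
| Visits 1–5 | about 10–23% | 0.2–7.0% |
| Visit 6 (last) | 0.9–5.1% | 0.9–8.9% |

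Hand check of one scenario (2% per visit, a = 50%, b = 0, about 12.1 of 250 ever retreated). At visit 1, 250 × 0.02 = 5 recur and half of them, 2.5, are later re-ablated. The columns show 2.5/12.1 = 20.7% and 2.5/237.9 = 1.1%, against 5/250 = 2.0% unsplit. The simulation gave 21.0% and 1.0% with persistent recurrences. Nobody has been retreated at that visit, so the whole gap comes from looking ahead.

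At the last visit a newly seen recurrence cannot yet have been retreated, and untreated recurrences may have accumulated among the never-retreated. The gap then closes or turns round: in the persistent version of the same scenario it is 3.8% against 6.9%.

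**The case against.** The strongest reply has four parts.

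1. **Ever/never is inferred.** SAP 8.6.4 does not say when status is determined, SAP 8.8.2 counts subsequent cryoablation separately for each visit, and the table shells are a separate document. This stands as a caution. Ever/never is nevertheless the natural reading, since the same list fixes the visit for the Hounsfield-unit subgroup and not for this one.

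2. **Repeat cryoablation need not follow recurrence.** SAP 8.7.1 counts baseline lesions left untreated, and SAP 8.8.1 counts new ipsilateral and contralateral lesions; either could be the later target. This stands. It raises b and weakens the effect, which disappears only if retreatment is unrelated to recurrence.

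3. **The output is minor.** It is descriptive and untested; the only test in SAP 8.6.4, Fisher's exact test, concerns the Hounsfield-unit flag. The unsplit percentages and the Kaplan-Meier time to recurrence (SAP 8.6.6) do not use this split, and the SAP never calls the never-retreated column a single-treatment rate. This stands, and it limits the weight of the point.

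4. **The direction is not guaranteed at every visit.** This also stands, as the last-visit results show.

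A reader might infer something stronger: that the retreated column will show near-universal failure. With 20 recurrences in 250 (8.0%), 12 of them re-ablated and 3 others re-ablated, the split is 12/15 = 80% against 8/235 = 3.4%. With 16 and 2 it is 16/18 = 89% against 4/232 = 1.7%. Those counts are assumed and the percentages are cumulative. SAP 8.6.4 plans no cumulative subgroup table, so they do not describe its output.

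**Conclusion.** The point holds in a limited form. As written, the split has no time anchor, and on its natural reading it conditions on a later event. If repeat cryoablation is likelier after recurrence, the never-retreated column understates recurrence after a single treatment and the retreated column overstates it at most visits; at the last visit the gap can vanish or reverse. The premise is supported by Protocol 7.5, which collects retreatment with progression, and by SAP 8.8.2, which treats subsequent cryoablation as renal cancer therapy, but neither states it as a rule.

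The size cannot be determined from the documents. The 10–23% against 0.2–7.0% at visits one to five rests wholly on the assumed rates and on retreatment clearing the lesion. The documents do not support a claim that the rates are distorted in a fixed direction at every visit, nor that the registry's main recurrence results are affected. This is a cheap improvement to one descriptive table.

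**What to change.** Either of two changes to SAP 8.6.4 would do.

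- **Anchor the split.** State that each patient is classified at each visit by whether repeat cryoablation had already occurred before that assessment. This removes the dependence on future events. A footnote should say that the not-yet-retreated group at later visits no longer contains earlier failures that were re-ablated, so the columns are not a comparison of treatments.
- **Replace the split with two summaries ordered in time.** (a) In all patients, the number with recurrence or progression with enhancement before any repeat cryoablation, and how many of those were re-ablated. (b) In re-ablated patients only, lesion status at visits counted from the date of the repeat cryoablation.

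The cost is a few lines of SAP text and one revised table shell. No new data are needed: SAP 8.6.4 already requires retreated patients to be identified manually, and the durations in SAP 8.8.2 already require their retreatment dates. The downside is that the retreated group will be small; under the simulated assumptions it was about 4 to 23 of 250 patients.

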8.6.5 Post-cryoablation biopsy

The number and percentage of patients with a “Yes” response (as defined in Section 6.4.3) will be given. A 95% CI for the percentage will be computed using the method of Wilson (1927).

8.6.6 Analysis of Time-to-Event Endpoints

Rates will be derived from the Kaplan-Meier estimates; 6, 12, 24, 36, 48 and 60 month rates will be presented, together with 95% CIs computed using the log-log transformation methodology of Kalbfleisch and Prentice (1980). Quartiles will be presented and 95% CIs will be calculated on the quartiles using the methodology of Brookmeyer and Crowley (1982) using the log-log standard error. Plots of the Kaplan-Meier curve will be provided showing the number of patients at risk at the date of treatment (i.e., 0 months), and at 6, 12, 24, 36, 48 and 60 months after treatment.

8.6.6.1 Time to Recurrence (TTR)

TTR will be computed as

$$\text{TTR (Months)} = (\text{Date of event/censor} - \text{Date of cryoprocedure} + 1) / 30.4375.$$

Censoring will be performed in the following order:

- 1) If a patient does not have a baseline lesion assessment, then the TTR time will be censored at the date of cryoprocedure, regardless of whether or not recurrence was observed after treatment.
- 2) If a patient has recurrence but has two or more missing lesion assessment visits (according to the 6 to 60 month analysis visits in Section 6.2.2) immediately before recurrence was observed, the TTR time will be censored at the date of the post treatment lesion assessment that occurred immediately before the first of the missed visits. For example, if a patient had a lesion assessment at Month 6, but did not have an assessment at Months 12 and 24, and then had recurrence at the Month 36 assessment, then the TTR time would be censored at the date of the Month 6 assessment.
- 3) If a patient is known not to have recurrence, the TTR time will be censored at the last date of lesion assessment date, or at the date of cryoprocedure if the patient does not have any post-treatment lesion assessments.

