6.4.4 Disease recurrence

Time to recurrence (TTR) is defined as the time from date of cryoprocedure to disease recurrence with enhancement in at least one lesion. A lesion is considered to have disease recurrence if the response to the question “What is the status of the lesion?” in the follow-up lesion assessment eCRF page, is “Recurrent”, and there is a “Yes” response to the related question, “If Progressing or recurrent, was the lesion identified by contrast enhancement?”

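### TTR censoring rule 1 sets aside observed recurrences when the baseline lesion assessment is missing, although the TTR event uses no baseline value

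*SAP*

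**What the plan says.** SAP 8.6.6.1 introduces three rules with "Censoring will be performed in the following order". Rule 1 comes first. Its trigger is "If a patient does not have a baseline lesion assessment", and its consequence is "then the TTR time will be censored at the date of cryoprocedure, regardless of whether or not recurrence was observed after treatment". Rule 2 deals with a recurrence that follows two or more missed assessment visits. Rule 3 deals with patients known not to have recurrence, including those with no post-treatment lesion assessment.

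The event is defined in SAP 6.4.4: "Time to recurrence (TTR) is defined as the time from date of cryoprocedure to disease recurrence with enhancement in at least one lesion". It is read from the status of the lesion and the contrast-enhancement question, both on the follow-up page: "in the follow-up lesion assessment eCRF page, is “Recurrent”, and there is a “Yes” response to the related question". SAP 5.2 records that progression no longer counts as a TTR event.

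Protocol 8.5 (Analyses) censors subjects without recurrence or progression, at last visit or death. It sets no baseline condition. SAP 5.2 lists the changes from the planned analyses, but rule 1 is not among them.

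**The concern.** A rule of this kind fits an endpoint measured as change from a baseline value, because without the baseline the event cannot be judged. The TTR event is different: it is a status recorded by the investigator at follow-up, together with a yes on contrast enhancement. A patient can meet the SAP's own definition in full and still be treated as never having been observed after the day of the procedure.

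At stake are the recurrence events and follow-up time that such patients bring to the 6- to 60-month Kaplan-Meier rates (SAP 8.6.6) and to the Cox models (SAP 7.2). The rule also works as an exclusion that is not described as one: these patients stay in the analysis population but add nothing after day 1.

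**Working it through.** **1. What rule 1 does to one patient.** SAP 8.6.6.1 computes TTR in months as (date of event or censoring − date of cryoprocedure + 1) / 30.4375. SAP 6.2.1 agrees on the numbering: "The date of cryoprocedure will be considered relative day 1". A rule-1 patient therefore has TTR = (0 + 1) / 30.4375 = 0.033 months, censored. The patient has left the risk set before any later event, so a recurrence recorded at month 12 or month 36 adds nothing to the Kaplan-Meier estimate or the Cox model.

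**2. Whether the event needs a baseline value.**

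| Source | Content | Baseline value needed? |
|---|---|---|
| SAP 6.4.4 | Two follow-up eCRF answers: recurrent, and identified by enhancement | No |
| SAP 5.2 | Progression removed from the TTR event | No |
| Protocol 8.5 | Only subjects without the event are censored | No |
| SAP 8.6.6.1, rule 1 | Day-1 censoring even with an observed recurrence | Yes |

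Rule 1 stands alone.

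**3. Loss of precision.** The documents give no event rate, power calculation or count of patients without a baseline assessment, so there is no stated figure to reproduce. Planned N is 250 (SAP 4.4). Assume that k patients are affected and that the standard error scales with one over the square root of the number of patients contributing. The inflation is 1/√(1 − k/250) − 1:

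- k = 5 (2%): 1/√0.98 − 1 = 1.0%
- k = 10 (4%): 1/√0.96 − 1 = 2.1%
- k = 20 (8%): 1/√0.92 − 1 = 4.3%

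**4. Effect on the rate.** Assume 250 patients, no other censoring, and 10% recurrence at 60 months among patients with a baseline assessment. Rule 1 then always reports 10.0%. With m patients lacking a baseline assessment and recurrence p among them, the rate in all patients is [(250 − m) × 0.10 + m × p] / 250.

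| m | p = 5% | p = 10% | p = 20% |
|---|---|---|---|
| 5 | 9.9% | 10.0% | 10.2% |
| 12 | 9.8% | 10.0% | 10.5% |
| 25 | 9.5% | 10.0% | 11.0% |
| 50 | 9.0% | 10.0% | 12.0% |

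At p = 10% the rate does not move; only events are lost, m × 0.10 = 0.5, 1.2, 2.5 and 5.0 in expectation.

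**5. A single data set.** Take 250 patients with 25 recurrences (10.0%), of whom 13 have no baseline assessment. Rule 1 leaves 250 − 13 = 237 patients contributing.

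- If 5 of the 13 recurred, 20 events remain: 20/237 = 8.4%.
- If 1 of the 13 recurred, 24 events remain: 24/237 = 10.1%.

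The estimate can move either way.

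**The case against.** **The group may be small or empty.** Protocol 7.1 collects baseline imaging on all subjects, SAP 6.3 accepts any assessment on or before the procedure day, and Protocol 9.2 has eCRFs checked and queried. This stands, and it limits the weight of the point. SAP 4.4 also says that the study is not powered for formal analysis.

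**The rule may have a reason.** SAP 6.4 says that the local judgement may rest on an increase in lesion size. SAP 6.5.1 foresees baseline lesions that were not treated, so without a baseline record it may be harder to tie a recurrent lesion to a treated one. That is a possible rationale, but the SAP does not give it. SAP 6.4.4 asks only for two follow-up answers in at least one lesion, and Protocol 7.2 separately collects lesion size and location, as available, at or before the procedure.

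**Stronger readings that the documents do not support:**

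- *The rule makes recurrence look rarer.* Rule 1 also removes patients without recurrence. If a missing baseline is unrelated to recurrence the rate is unchanged, and otherwise the direction is not fixed.
- *The recurrences vanish from the report.* SAP 8.6.4 tabulates "The number and percentage of patients with post-cryoablation lesion recurrence with enhancement" by visit with no baseline condition, SAP 7.1 lists all data, and SAP 8.1 requires a breakdown of censoring reasons. The loss is confined to the TTR analyses.
- *Rule 1 is why the visit-wise table and TTR would disagree.* They can differ without it: for patients with multiple lesions SAP 6.4.2 takes the largest, whereas TTR counts any lesion, and rule 2 also censors some recurrences.
- *Rule 1 alone inflates the number at risk at 0 months.* Rule 3 does the same for patients with no post-treatment assessment.

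**Conclusion.** The point holds for the TTR analyses. Rule 1 discards events that meet the SAP's own definition, gives no reason, and departs from Protocol 8.5 without an entry in SAP 5.2. That much rests on the text alone.

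The size is unknown. Under the assumption of 5 to 20 affected patients out of 250, the loss of precision is modest, at about 1.0% to 4.3% in the standard error. Bias arises only if a missing baseline is related to recurrence. In the illustrations that assume 10% recurrence among patients with a baseline, the rate in all patients ranged from 9.0% to 12.0% against a reported 10.0%, and those extremes required 50 of 250 patients to lack a baseline assessment. The change is worth making because it is clear and cheap; the documents do not show that the effect is large.

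**What to change.** - Delete rule 1 from SAP 8.6.6.1.
- State that an observed recurrence is an event at its own date, subject to rule 2 as it stands. Rule 3 cannot carry this, because it covers only patients known not to have recurrence.
- Censor patients without recurrence under rule 3, which already handles those with no post-treatment assessment.
- Keep the rule-1 version at most as a sensitivity analysis, and report how many patients it affects and how many of them had a recurrence.
- If rule 1 is kept as primary, give the reason and list the departure from Protocol 8.5 in SAP 5.2.

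The cost is about one sentence in the SAP and one line of programming. No new data are needed. The reported recurrence rate may move in either direction or not at all.
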